2.7 Patient Information and Informed Consent

The investigators will explain to each participant the nature of the study, its purpose, the procedures involved, the expected duration, the potential risks and benefits, any discomfort it may entail and grant enough time for consideration. Each participant will be informed that the participation in the study is voluntary and that he/she may withdraw from the study at any time and that withdrawal of consent will not affect his/her subsequent medical assistance and treatment. The participant must be informed that his/her medical records may be examined by authorised individuals other than their treating physician.

All participants for the study will be provided a participant information sheet and a consent form describing the study and providing sufficient information for participant to make an informed decision about their participation in the study.

The patient information sheet and the consent form will be submitted to the CEC and to the competent authority to be reviewed and approved. The formal consent of a participant, using the approved consent form, must be obtained before the participant is submitted to any study procedure.

The participant should read and consider the statement before signing and dating the informed consent form, and should be given a copy of the signed document. The consent form must also be signed and dated by the investigator and it will be retained as part of the study records.

Please refer to appendix for a copy of the Patient Information Brochure.

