5. STUDY OUTCOMES

5.1 Primary outcome

Any development of VAS/NRS score > 3 , in hourly measurements within the first four hours after completion of bariatric surgery.

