6. STUDY DESIGN

6.1 General study design and justification of design

The study design will be randomized, double blinded and placebo controlled. All patients complying our inclusion criteria will be included to the selection procedure. Patients will be informed about the study sequence during preoperative anesthesiological consultation to give their informed consent. Patients` data will be subsequently integrated to the eCRF. Each participant will be linked with a unique identification code which will be used for continuing process. Furthermore, information about sex, date of birth, date of surgery, indication, BMI, ASA classification, medical history and allergies will be recorded. Patients denying informed consent will be excluded from the pool of selected patients.

The intervention to be studied will either be the additional application of systemic lidocaine 1% dosed 1.5 ml/kg LBM to general anesthesia in bariatric surgery or the application of placebo. Patients, randomly assigned to one study group, will be surveyed for 48 hours after completion of surgery, experienced pain, occurrence of PONV, time to first defecation and length of hospitalization will be monitored. The population to be studied will include 140 patients listed for bariatric surgery at the Kantonsspital St. Gallen and fulfilling criteria for inclusion, respectively without criteria for exclusion. Patients, medical practitioner, nurses and investigators will be blinded by utilization of equal appearance and packing of IMPs, which will be fabricated individually for each patient and on request one to two days before surgery by the pharmacy of the Kantonsspital St. Gallen. Each patient will self-evaluate his maximal experienced pain eight-hourly during a sequence of 48 hours after completion of surgery. Study observation ends with study nurses` final visit on second postoperative day 2pm respectively +/- 30 minutes.

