7.5 Criteria for withdrawal / discontinuation of participants

The criteria for withdrawal of participants are either the request of participants to be withdrawn from the study or SAE, related to exercise of IMPs or other medication applied during general anesthesia, including signs of cardiac arrhythmia or other evidence of drug incompatibility resulting in hemodynamic instability.

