8.5 Dose modifications

If SAE will be recognized, infusion of investigational product will be stopped and arrangements conducted to treat potential adverse effects and ensure patients` safety. The Principal Investigator will be informed about the incident within 24 hours.

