9.4 Procedures at each visit

Each patient will be visited after surgical treatment and transfer to PACU/ICU by a study nurse or the Study Investigator. The VAS/NRS score (registration of any development of VAS/NRS score > 3) will be assessed by trained nurse practitioners in the PACU/ICU in hourly measurements during the first four hours after completion of surgery, respectively until discharge to the surgical ward. Thereafter, VAS/NRS score will be assessed by a patient questionnaire for self-evaluation and in addition by trained nurse practitioners during their daily round (10am and 2pm respectively ± 30 minutes) during the first four hours and during 48 hours after completion of surgery. VAS/NRS scores and vital parameters will be recorded. Incidental questions about upcoming study process will be answered. Infusion of the investigational product will be stopped four hours after the end of surgery (or before the transfer of the patient from the PACU to the surgical ward, whichever occurs first). Pain evaluation will take place every eight hours by recording the maximum VAS/NRS score experienced within this period. Recording of VAS/NRS scores will be stopped at 2pm respectively ± 30 minutes on second postoperative day. Completion of study investigation will be finalized by collecting the study documents at study nurses final visit on second postoperative day at 2pm respectively ± 30 minutes.

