10.4 Planned Analyses

Following populations will be analyzed

- Interventional group (patients receiving lidocaine 1% I.V. in addition to general anesthesia)
- Control group (patients receiving saline 0.9% as placebo I.V. in addition to general anesthesia)
- whole population (evaluation of secondary endpoints)

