10.8 Handling of missing data and drop-outs

Missing postoperative VAS/NRS scores, required for primary and secondary endpoints, will be handled as interpolation values, calculating an average score between last recorded scores before and after the missing value. Missing data for secondary endpoint PONV or time to first defecation will be handled as no occurrence of PONV (PONV 0) or no defecation yet. In case of drop-out, data collected till patients drop out will be neglected and not taken into account of statistical consideration of the study.

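### Section 10.8 drops all data of any drop-out, even when the four-hour primary outcome is already recorded, and no as-randomised primary set or sensitivity analysis is named

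*Combined protocol and SAP*

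**What the plan says.** The exclusion is in section 10.8: "In case of drop-out, data collected till patients drop out will be neglected and not taken into account of statistical consideration of the study". It carries no exception, and drop-out is not defined there or elsewhere.

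The primary outcome (section 5.1) is any pain score above 3 "in hourly measurements within the first four hours after completion of bariatric surgery". Observation lasts much longer: section 6.1 ends it at the study nurses' "final visit on second postoperative day 2pm respectively +/- 30 minutes", and section 9.4 agrees: "Completion of study investigation will be finalized by collecting the study documents at study nurses final visit on second postoperative day". Section 2.7 tells patients that "he/she may withdraw from the study at any time".

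Section 7.5 gives as withdrawal criteria the participant's request "or SAE, related to exercise of IMPs or other medication applied during general anesthesia". For an SAE, section 8.5 says only that "infusion of investigational product will be stopped and arrangements conducted" for treatment and safety. Neither section mentions section 10.8.

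Section 10.4 describes the comparison groups by product received, for example "Interventional group (patients receiving lidocaine 1% I.V. in addition to general anesthesia". It also lists a whole population, undefined and tied to the secondary endpoints. Section 10.5 names tests but no analysis set.

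**The concern.** A patient who scores 6 at hour 1 and withdraws the next day has a known primary outcome: an event. Section 10.8 removes that patient. The same holds for a patient with four scores of 3 or less who leaves on day 1.

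Randomisation protects the comparison only while patients stay in the analysis regardless of what happens afterwards. Pain or side effects can prompt withdrawal, so exclusion after randomisation may be related to outcome or treatment. Since no as-randomised analysis is planned, a reader of the results could not tell whether a borderline finding depends on who was left out.

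**Working it through.** **1. The plan's own figures.** Inputs: 65% v 35% (section 10.2); two-sided 0.05, 90% power, 63 per group, 10% drop-out, 140 in total (section 10.3); 1:1 allocation (section 6.3).

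- Uncorrected: n0 = [1.960·√(2·0.5·0.5) + 1.282·√(0.65·0.35 + 0.35·0.65)]² / 0.30² = 56.3, so 57.
- Continuity-corrected: n = (n0/4)·[1 + √(1 + 4/(n0·0.30))]² = 62.8, so 63. This matches the plan.
- 63/0.9 = 70 per arm, 140 in total.

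The synopsis adds the 10% to the 63 per group, so the allowance is about 7 losses per arm.

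**2. How many known outcomes could be lost.** At most about 7 per arm if every loss comes after hour 4 or after a first score above 3. It is fewer if some come before surgery, because recruitment is two to three weeks before hospitalisation (section 7.3). The documents give no timing or reasons.

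**3. Effect on the test.** The rejection probability is the sum, over all pairs of event counts (a, b), of Bin(a; n_L, p_L)·Bin(b; n_P, p_P) for which the chi-square statistic is at least 3.841. Section 10.5 does not say whether the test is continuity-corrected, so both versions are shown. Rows 4, 5 and 7 are assumed scenarios, not estimates; in them placebo losses are random.

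| Situation | Lidocaine rate | Placebo rate | n per arm | Uncorrected | Corrected |
|---|---|---|---|---|---|
| 1. Planned effect, nobody excluded | 0.35 | 0.65 | 70 | 95.2% | 93.3% |
| 2. Planned effect, 7 random losses per arm | 0.35 | 0.65 | 63 | 93.7% | 91.5% |
| 3. No effect, 7 random losses per arm | 0.65 | 0.65 | 63 | 5.1% | 3.2% |
| 4. No effect, all 7 lidocaine losses are events | (45.5 − 7)/63 = 0.611 | 0.65 | 63 | 7.7% | 5.2% |
| 5. As row 4, but 4 late losses per arm | (45.5 − 4)/66 = 0.629 | 0.65 | 66 | 6.0% | 3.9% |
| 6. No effect, all 7 losses in both arms are events | 0.611 | 0.611 | 63 | 5.5% | 3.5% |
| 7. Planned effect, all 7 lidocaine losses are non-events | 24.5/63 = 0.389 | 0.65 | 63 | 85.8% | 82.0% |

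Here 45.5 = 70·0.65 and 24.5 = 70·0.35 are the expected events among those randomised. Rows 1, 2 and 7 are power; rows 3 to 6 are type I error.

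**4. Would a single result change?** Uncorrected chi-square, X² = N(ad − bc)² / (product of the four margins), lidocaine first; corrected p in brackets.

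- Planned size, 22/63 v 41/63: X² = 126·1197²/63⁴ = 11.46, p = 0.0007 (0.0013).
- The same with 7 lidocaine events restored, 29/70 v 41/63: X² = 133·1043²/(70·63·70·63) = 7.44, p = 0.006 (0.011).
- Borderline (assumed), 29/63 v 41/63: X² = 126·756²/(63·63·70·56) = 4.63, p = 0.031 (0.049).
- The same with 3 lidocaine events restored, 32/66 v 41/63: X² = 129·690²/(66·63·73·56) = 3.61, p = 0.057 (0.085).

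**The case against.** The best defence is that drop-out may be meant for patients lost before the outcome. Section 7.3 and table 2 place consent and randomisation at the preoperative consultation, so many losses may be cancelled or postponed operations with no outcome to discard. After surgery patients are on the PACU and ward, and late withdrawals may be few. This limits the number affected, and row 5 shows how quickly the effect shrinks. It does not repair the rule, which speaks of data already collected and makes no distinction by timing.

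On treatment-related loss, a reader might infer that lidocaine patients with drug-related SAEs are removed and the comparison thereby tilted. The documents do not support that as a fact. Section 10.8 does not refer to section 7.5, section 8.5 speaks only of stopping the infusion, and sections 3.2 and 3.5 report no evidence of added risk and a comparable rate of adverse effects with placebo. The trial is also double-blind. What stands is that the possibility is left open.

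A reader might also take section 10.4 as a plan to analyse by treatment received. Its wording may be merely descriptive, since sections 6.3, 7.4 and 8.1 form the groups by random allocation. The fair statement is that no as-randomised set is named.

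Finally, all 14 losses falling in the lidocaine arm, all of them events, would give a type I error of 17.1%. That departs from the allowance of about 7 per arm and should not be read as the plan's risk. The 10% inflation, for its part, protects numbers but not comparability.

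**Conclusion.** The concern holds as a defect in the primary analysis set and should be fixed. Followed exactly, section 10.8 discards known primary outcomes and permits exclusions after randomisation that could be related to outcome or treatment, and nothing else in the protocol would reveal their influence.

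The likely size is modest. Random loss causes no bias, only a small loss of precision. Even when every lidocaine loss at the planned rate is assumed to be an event, the corrected test, which is the version that reproduces the planned 63, stays close to 5%. The opposite extreme costs about 8 points of power (9.5 corrected). Neither extreme is a forecast: both assume that all losses come after the outcome is known, that they are wholly selected on outcome in the lidocaine arm, and that they are random under placebo. It would be wrong to conclude that the trial is biased in favour of lidocaine or that a result of the planned size would be unsafe. The exposure is to a smaller, borderline difference, where three restored patients can move the result across 0.05.

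**What to change.** Replace the last sentence of section 10.8 and amend section 10.4 to state:

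1. The primary analysis includes all randomised patients in the arm assigned, excluding at most those who never had surgery, with that decision made blind to arm. Define the whole population.
2. Data recorded before withdrawal are kept unless the patient refuses their use. Any recorded score above 3 within four hours is an event; four recorded scores all at or below 3 are a non-event.
3. Drop-out is defined for the analysis and distinguished from stopping the investigational product. Sections 7.5, 8.5 and 10.8 must be reconciled on this.
4. Primary outcomes still unresolved are handled by one pre-stated method, with one pre-stated sensitivity analysis (for example, counting missing as an event).

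Section 10.7 already provides for such changes by amendment. The cost is wording, a little more analysis and possibly mild dilution of the effect; no extra patients are needed. Hourly scoring after early transfer to the ward, interpolation of single missing scores, and safety summaries are separate matters and not part of this point.

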11. SAFETY ANALYSIS

11.1 Drug studies

During the entire duration of the study, all AE, ADR and all SAE, related to the application of IMPs (severity of possible AE related to lidocaine will be discussed in chapter 11.6) are collected, fully investigated and documented in source documents and case report forms (CRF). Study duration encompassed the time from when the participant signs the informed consent until study nurses final visit on second postoperative day at 2pm respectively +/- 30 minutes.

11.2 Definition and assessment of (serious) adverse events and other safety related events

An AE is any untoward medical occurrence in a patient or a clinical investigation participant administered a pharmaceutical product and which does not necessarily have a causal relationship with the study procedure. An AE can therefore be any unfavourable and unintended sign (including an abnormal laboratory finding), symptom, or disease temporally associated with the use of a medicinal product, whether or not related to the medicinal product.

A **SAE** is classified as any untoward medical occurrence that:

- results in death
- is life-threatening
- requires in-patient hospitalization or prolongation of existing hospitalization
- results in persistent or significant disability/incapacity
- is a congenital anomaly/birth defect

In addition, important medical events that may not be immediately life-threatening or result in death, or require intensive care treatment, but may require intervention to prevent one of the other outcomes listed above should also usually be considered serious.

SAE should be followed until resolution or stabilization. Participants with ongoing SAE at study termination (including safety visit) will be further followed up until recovery or until stabilization of the disease after termination.

11.3 Assessment of Causality

Both Investigator and Sponsor-Investigator make a causality assessment of the event to the study drug, based on the criteria listed in the ICH E2A guidelines:

Relationship	Description
Definitely	Temporal relationship; Improvement after dechallenge; Recurrence after rechallenge (or other proof of drug cause)
Probably	Temporal relationship; Improvement after dechallenge; No other cause evident
Possibly	Temporal relationship; Other cause possible
Unlikely	Any assessable reaction that does not fulfil the above conditions
Not related	Causal relationship can be ruled out

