9.3 Assessments of safety outcomes

Vital parameters (blood pressure, pulse rate, oxygen saturation) will be recorded digitally by the electronic acute care patient data management system (ACPDMS) during the peri- and postoperative phase and according to institutional standards.. During the entire surgical and anaesthetic procedure and in the PACU trained personnel will be present monitoring vital parameters and the patient clinical status. Every deviation to normal course will be treated and recorded according clinical standards of the institution. SAE related to the administration of the IMP will cause an immediate cessation of the drug administration and will be reported to the Sponsor Investigator not later than 24 hours after the event.

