11.5 Suspected Unexpected Serious Adverse Reactions (SUSAR)

The Sponsor Investigator evaluates any SAE that has been reported regarding seriousness, causality and expectedness. If the event is related to the investigational product and is both serious and unexpected, unblinding will be carried out by the Sponsor Investigator to re-evaluate the event and eventually classify it a SUSAR. In this case, the Sponsor Investigator will give report including full detail about patient and incident to the local ethics committee within 15 days. In case of fatal SUSAR, reporting to local ethics committee will be given within seven days. Swissmedic will be informed about non-fatal SUSAR within 15 days and in case of fatal SUSAR within seven days.

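### The causality table in section 11.3 has no row for an event that follows the drug, has other causes excluded and shows no improvement on dechallenge; read literally it is graded Unlikely and can bypass SUSAR handling

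*Combined protocol and SAP*

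**What the plan says.** Section 11.3 has the Investigator and the Sponsor-Investigator each grade causality on five levels. The criteria are:

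- The top grade, *Definitely*, has three conditions: "Temporal relationship; Improvement after dechallenge; Recurrence after rechallenge (or other proof of drug cause" (the bracket closes after the last word).
- The next grade, *Probably*, keeps the first two of these and swaps the third for the absence of another evident cause.
- The middle grade, *Possibly*, drops dechallenge and is worded "Temporal relationship; Other cause possible".
- The residual grade, *Unlikely*, takes whatever is left: "Any assessable reaction that does not fulfil the above conditions".
- The lowest grade, *Not related*, is for events where causality is excluded.

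Section 11.5 makes the SUSAR process depend on relatedness: "If the event is related to the investigational product and is both serious and unexpected, unblinding will be carried out by the Sponsor Investigator". Reports then go to the ethics committee and to Swissmedic, within seven days for a fatal SUSAR and within 15 days otherwise. Neither 11.3 nor 11.5 says which of the five grades count as related.

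**The concern.** A causality scale should not rate an event lower because the alternative explanations have been removed. In this table, once improvement after dechallenge is missing, the only upper grade still open is *Possibly*, and that grade is defined by another possible cause. Excluding the other cause therefore pushes the event down into the residual row.

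Dechallenge is uninformative in several situations that the protocol itself provides for. Section 11.2 lists death and persistent disability as SAE criteria. The IMP begins with one bolus, which cannot be withdrawn. The infusion ends at the latest four hours after surgery (8.1, 8.4), while adverse events are recorded to the second postoperative day and at the follow-up on day seven or at discharge (table 2, 11.8). A later-onset event therefore has no infusion left to stop.

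At stake is whether a serious, unexpected event with no other explanation is unblinded, classified as a SUSAR and reported as one. The trial has no data safety monitoring committee (1.3), and 11.3 is the only causality scale in the document.

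**Working it through.** There is no figure in the plan to reproduce. The check applies the table as a decision rule.

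**Inputs.** The five rows of 11.3, with the conditions in a row joined by AND. An OR reading would make every temporally related event *Definitely*, which is untenable. Hold fixed: temporal relationship present, no rechallenge, no other proof of drug cause, causality not ruled out. Take the highest row that is met.

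**Two terms to keep apart.** *Probably* speaks of a cause being evident, *Possibly* of a cause being possible. These are not opposites, since a cause can be possible without being evident. Other cause therefore needs three states, and dechallenge also has three, giving 3 × 3 = 9 combinations:

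| Improvement after dechallenge | Other causes excluded | Other cause possible, not evident | Other cause evident |
|---|---|---|---|
| Yes | Probably | Probably | Possibly |
| No | Unlikely | Possibly | Possibly |
| Cannot be assessed | Unlikely | Possibly | Possibly |

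Count: *Probably* 2, *Possibly* 5, *Unlikely* 2 (2 + 5 + 2 = 9). In the second and third rows, moving left to remove the competing cause lowers the grade from *Possibly* to *Unlikely*. In the first row, removing it raises the grade from *Possibly* to *Probably*, as it should.

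**Sensitivity of the two *Unlikely* cells to the reading of the table.**

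- If other proof of drug cause substitutes only for rechallenge, improvement is still required, and the event stays *Unlikely* even with such proof.
- If other proof alone suffices, the event becomes *Definitely*, but only where that proof exists.
- If a possible other cause is treated as never excluded, the event becomes *Possibly*, equal to the competing-cause event, and the inversion disappears.

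**Tracing the grade into 11.5, if *Unlikely* is treated as not related.**

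- Fatal event: unblinding, SUSAR classification and the seven-day report to Swissmedic can be missed. The ethics committee still learns of the death within a week under 11.7, whatever the grade.
- Non-fatal irreversible event: the same steps can be missed, and so can the 15-day SUSAR reports to both the ethics committee and Swissmedic.

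**The case against.** The strongest reply has four parts.

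1. **Few events can reach the gap.** Bariatric patients receive several anaesthetic drugs besides the IMP and undergo surgery. Another cause will nearly always remain possible, and the event is then *Possibly*. This stands. A reader might infer that every fatal event without an evident other cause is graded *Unlikely*; the text does not support that, because a cause that is not evident may still be possible.

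2. **Other rules do not depend on the grade.** The Sponsor Investigator evaluates any reported SAE (11.5). Deaths go to the ethics committee within a week, and safety signals to the ethics committee and Swissmedic within seven days (11.7). Section 11.9 collects all SAEs. This also stands. A reader might infer that a fatal event would be lost, that the infusion would continue, or that the event would fail to count as an SAE. None of these follows: 8.5 stops the infusion and informs the Principal Investigator within 24 hours for any recognised SAE, and under 11.2 death and persistent disability are SAEs whatever their cause. What these routes do not replace is SUSAR unblinding, classification and reporting, because the evaluation in 11.5 includes causality and 11.3 supplies the scale for it. The collection route is also less firm than it looks, since 11.1 can be read as limiting SAE collection to related events.

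3. **The cut-off may be defined elsewhere.** Section 11.3 says that its criteria rest on ICH E2A, and 11.9 refers to sponsor SOPs. That is possible and cannot be checked here. It would answer the missing cut-off, but it would not repair the row structure in the protocol's own table.

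4. ***Unlikely* covers only assessable reactions.** Whether that includes a reaction whose dechallenge cannot be judged is unclear. If it does not, the event has no grade at all, which is no better. The case of assessed non-improvement is unaffected.

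A reader might also infer that disagreement between the two assessors is left open. Sections 11.5 and 11.7 largely answer this by giving the re-evaluation to the Sponsor Investigator.

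**Conclusion.** The concern holds in a limited form. On the literal text, 2 of the 9 combinations with a temporal relationship receive a grade below that of a weaker case. These are the two in which other causes are excluded and improvement is absent or cannot be assessed. An assessor can avoid the result by reading the *Possibly* row permissively or by relying on other proof, but the table does not say so.

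The consequence is confined to 11.5: possible loss of unblinding, SUSAR classification, the SUSAR report to Swissmedic and, for non-fatal events, the SUSAR report to the ethics committee. It rests on two assumptions: that the table is applied as written, and that *Unlikely* is treated as not related. The documents do not state the second. The number of events will be small, but they are among the most serious. The table should be corrected; the efficacy analyses are not touched.

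**What to change.** In 11.3:

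- Extend *Possibly* so that a temporal relationship is enough when either another cause is possible or improvement after dechallenge is absent or cannot be assessed.
- Define *Unlikely* positively: no plausible temporal relationship, or another cause clearly more likely. An event with a clearly more likely other cause would also meet *Possibly*, so state which row takes precedence.

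In 11.5, state that *Definitely*, *Probably* and *Possibly* count as related for SUSAR classification and reporting.

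With these changes both *Unlikely* cells become *Possibly*, and excluding a competing cause no longer lowers the grade. The cost is an edit to one table, one added sentence and matching text on the SAE form. The small downside is that slightly more events will be handled as related.

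Separately, 8.5 applies the infusion stop to any recognised SAE, whereas 9.3 words it as "SAE related to the administration of the IMP will cause an immediate" cessation. The sponsor should reconcile the two sections; no stopping rule is proposed here.
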